11. **For the dose-escalation portion**, patients with solid tumors with alterations that may be associated with antitumor activity based on preclinical data for BDTX-189 such as:

- a. [REDACTED] or [REDACTED] mutation(s)
- b. [REDACTED] or [REDACTED] mutation
- c. [REDACTED] amplified or overexpressing tumor
- d. [REDACTED] mutation

Mutations must have been determined by a validated NGS test routinely used by each institution using tissue and/or plasma and performed in a Clinical Laboratory Improvement Amendments (CLIA)-certified or equivalent laboratory. A list of eligible validated oncogenic mutations from 1 of the 7 MTCs is provided in [Appendix I](#).

Part A Safety Expansion Only

12. Patients with one of the following mutations and tumor pairs:

- a. [REDACTED] mutation in patients with NSCLC, breast cancer, biliary tract cancer, or cervical cancer
- b. [REDACTED] or [REDACTED] mutation in patients with NSCLC
- c. [REDACTED] amplified or overexpressing tumor from the following cancer types: breast, gastric, gastroesophageal, colorectal, endometrial, biliary tract, cancer of unknown primary (CUP), and NSCLC

Mutations must have been determined by a validated NGS test routinely used by each institution using tissue and/or plasma and performed in a CLIA-certified or equivalent laboratory. A list of eligible validated oncogenic mutations from 1 of the 7 MTCs are provided in [Appendix I](#).

Note: The Sponsor reserves the right to prioritize tumor/genomic alteration pairs and to cap enrollment for any of these based on the Sponsor's portfolio decision-making process.

13. Mandatory archival tumor tissue or willing to undergo pretreatment biopsy if no archival tissue available (Section [5.7.1](#)).

14. Measurable disease according to RECIST version 1.1 ([Appendix B](#)).

Part B Only

15. Patients with locally advanced or metastatic:

- a. NSCLC who have received at least one prior platinum-containing regimen (with or without an anti-PD-[L]1 antibody) and no more than 2 prior regimens for advanced NSCLC. Patients with no prior therapy who refuse standard therapy may also be eligible following discussion and approval by the Sponsor's Medical Monitor.
- b. Solid tumor other than NSCLC who have received at least one and no more than 3 prior regimens for advanced cancer.

16. Patients with solid tumor(s) harboring an:

- a. [REDACTED] mutation.
- b. [REDACTED] mutation or [REDACTED] mutation.

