Patients will be evaluated for response to treatment after 2 cycles of treatment. Response will be assessed at 6-week intervals (± 3 days) during the first 24 weeks (8 cycles) of study treatment. Thereafter, patients will be evaluated for response to treatment every 12 weeks (± 7 days), at the EOT visit (if not performed within the previous 4 weeks), and at the discretion of the Investigator. Patients with PD or unacceptable toxicity should be discontinued from the study; patients with SD or response to therapy will continue treatment. However, patients who are receiving clinical benefit in the opinion of the treating Investigator may be allowed to stay on study beyond initial radiological progression after consultation with the Medical Monitor if it is felt that it is in the patient's best interest. The assessments to be performed at this time are specified in [Appendix B](#). All target and non-target lesions documented at screening must be assessed. Please refer to Section [7](#) for further instructions on evaluating response (e.g., PD, SD).

The following assessments will be performed if abnormal at baseline or if clinically indicated:

- CT scan or MRI of chest, abdomen, and pelvis plus any other sites of known disease.
- CT scan head/MRI brain if history of CNS metastasis.

Investigators must ensure that images of all chest and abdomen CT/MRI scans for patients enrolled in Part B are available for transmission to the Sponsor for a future central reading by a BICR committee depending on preliminary efficacy results from Part A (see separate imaging charter).

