9.4. Analysis Population

The following analysis populations will be used:

- The Intent-To-Treat (ITT) population is defined as all patients who signed informed consent. The ITT population is the primary population for the summarization of enrollment.
- The Full Analysis (FA) population is defined as all patients who receive at least one dose of BDTX-189. The FA population is the primary population for both safety and Part A efficacy analyses.
- The Per-Protocol Efficacy (PPE) population is defined as all FA population patients who meet the eligibility criteria, receive BDTX-189, and have at least one baseline and post-baseline response assessment. The PPE population will be used for exploratory sensitivity analyses.

- The DLT-evaluable population will consist of all patients in Part A (excluding those patients in the Food-Effect Cohort) who receive at least 75% of the planned oral doses during Cycle 1 and complete all required safety evaluations or who have a DLT in Cycle 1.
- The Pharmacokinetic (PK) population is defined as all patients who receive at least one dose of BDTX-189 and have at least one post-dose PK blood collection with associated bioanalytical results.
- The Pharmacodynamic (PDx) population is defined as all patients who receive at least one dose of BDTX-189 and have post-baseline ctDNA samples or have paired on-treatment tumor tissue biopsy results.

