Efficacy analyses in Part A will be performed using the FA Population by cohort and combined. Part B efficacy summaries will be performed by cohort/subgroup.

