Target Lesions:	
The most reproducible measurable lesions, up to a maximum of 2 lesions per organ and 5 lesions in total, representative of all involved organs should be identified as target lesions and recorded and measured at baseline.
 
Target lesions should be selected on the basis of their size (lesions with the longest diameter), should be representative of all involved organs, and in addition should be those that lend themselves to reproducible repeated measurements. Pathological nodes which are defined as measurable and that may be identified as target lesions must meet the criterion of a short axis of ≥ 15 mm by CT scan.
 
A sum of the diameters (longest for non-nodal lesions, short axis for nodal lesions) for all target lesions will be calculated and reported as the baseline sum diameters. If lymph nodes are to be included in the sum, then as noted above, only the short axis is added into the sum. The baseline sum diameters will be used as reference to further characterize any objective tumor response.

Non-Target Lesions:	
All other lesions should be identified as non-target lesions at baseline. Measurements of these lesions are not required, but the presence or absence of each should be noted throughout follow-up.

Guidelines for Evaluation of Measurable Disease

All measurements should be taken and recorded in metric notation, using a ruler or calipers. All baseline evaluations should be performed as closely as possible to the beginning of treatment, as per protocol screening requirements.

The same method of assessment and the same technique should be used to characterize each identified and reported lesion at baseline and during follow-up. Imaging-based evaluation is preferred to evaluation by clinical examination when both methods have been used to assess the antitumor effect of a treatment.

Clinical Lesions:	Clinical lesions will only be considered measurable when they are superficial (e.g., skin nodules and palpable lymph nodes) and ≥ 10 mm in diameter. In the case of skin lesions, documentation by color photography, including a ruler to estimate the size of the lesion, is recommended.
Chest X-ray:	Lesions on chest X-ray are acceptable as measurable lesions when they are clearly defined and surrounded by aerated lung. However, a CT scan is preferable.

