Conventional CT and MRI:	CT, MRI: CT is the best currently available and reproducible method to measure lesions selected for response assessment. This guideline has defined measurability of lesions on CT scan based on the assumption that CT slice thickness is 5mm or less. When CT scans have slice thickness greater than 5 mm, the minimum size for a measurable lesion should be twice the slice thickness. MRI is also acceptable in certain situations (e.g., for body scans).
Ultrasound:	When the primary trial endpoint is objective response, ultrasound should not be used to measure tumor lesions. It is, however, a possible alternative to clinical measurements of superficial palpable lymph nodes, subcutaneous lesions, and thyroid nodules. Ultrasound may also be useful to confirm the complete disappearance of superficial lesions usually assessed by clinical examination.
Endoscopy and Laparoscopy:	Use of endoscopy and laparoscopy for objective tumor evaluation has not yet been fully and widely validated. Therefore, use of these techniques for objective tumor response should be restricted to validation purposes in specialized centers. Such techniques can be useful in confirming complete pathological response when biopsies are obtained.
Tumor Markers:	Tumor markers alone cannot be used to assess response. If markers are initially above the upper limit of normal, they must normalize for a patient to be considered in complete clinical response when all lesions have disappeared.
Cytology and Histology:	Cytology and histology can be used to differentiate between partial response (PR) and complete response (CR) in rare cases (e.g., after treatment to differentiate between residual benign lesions and residual malignant lesions in tumor types such as germ cell tumors).

Response Criteria

Evaluation of Target Lesions

Complete Response (CR): Disappearance of all target lesions.

Partial Response (PR): At least a 30% decrease in the sum of diameters of target lesions, taking as reference the baseline sum diameters.

Stable Disease (SD): Neither sufficient shrinkage to qualify for PR nor sufficient increase to qualify for PD, taking as reference the smallest (nadir) sum of diameters since the treatment started.

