Progressive Disease (PD): At least a 20% increase in the sum of the diameters of target lesions, taking as reference the smallest (nadir) sum since the treatment started, or the appearance of one or more new lesions. Requires not only 20% increase, but absolute increase of a minimum of 5 mm over sum.

Evaluation of Non-Target Lesions

Complete Response (CR): Disappearance of all non-target lesions and normalization of tumor markers. All lymph nodes must be non-pathological in size (<10 mm short axis).

Non-CR/Non-PD: Persistence of one or more non-target lesions and/or persistence of tumor marker level above the normal limits.

Progressive Disease (PD): Appearance of one or more new lesions and/or unequivocal progression of existing non-target lesions. When the patient also has measurable disease, to achieve “unequivocal progression” on the basis of the non-target disease, there must be an overall level of substantial worsening in non-target disease such that, even in presence of SD or PR in the target disease, the overall tumor burden has increased sufficiently to merit discontinuation of therapy.

Evaluation of Best Overall Response

The best overall response is the best response recorded from the start of the treatment until disease progression/recurrence (taking as reference for PD the smallest measurements recorded since the treatment started). In general, the patient's best response assignment will depend on the achievement of both measurement and confirmation criteria.

Confirmation of response (by repeat scans after 4 weeks or as specified in the protocol) is required for trials in which response rate is the primary endpoint but is not required in randomized trials or trials with primary survival endpoints (i.e., where response is not a primary endpoint).

Note that a best overall response of SD requires an assessment of SD or better at the time of the first protocol-specified post-baseline tumor assessment (i.e., 42 days +/- 3 days after first dose) or later.

Target Lesions	Non-Target Lesions	New Lesions	Overall Response
CR	CR	NO	CR
CR	NON-CR/NON-PD	NO	PR
CR	NE	NO	PR
PR	NON-CR/NON-PD OR NE	NO	PR
SD	NON-CR/NON-PD OR NE	NO	SD
NOT ALL EVALUATED	NON-PD	NO	NE
PD	ANY	YES OR NO	PD
ANY	PD	YES OR NO	PD
ANY	ANY	YES	PD

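### Part A ORR counts all dosed patients, but about 80 of 128 may enter without measurable disease; any who lack it cannot reach PR and would dilute the ORR

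*Combined protocol and SAP*

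**What the plan says.** **Analysis set.** Section 9.5.3: "Efficacy analyses in Part A will be performed using the FA Population by cohort and combined". Section 9.4 defines the set with no disease condition: "The Full Analysis (FA) population is defined as all patients who receive at least one dose of BDTX-189". It also gives the set its role: "The FA population is the primary population for both safety and Part A efficacy analyses".

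**Eligibility.** Section 3.1 lists "Measurable disease according to RECIST version 1.1" as criterion 14, under the block for the Safety Expansion only, and again as criterion 17 for Part B. It is not among criteria 1–9 (all patients), 10 (Part A) or 11 (dose escalation). The synopsis places it the same way. The Food-Effect cohort has no eligibility block of its own, and Table 1 groups it with dose escalation.

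**Response rules.** Appendix B draws target lesions from measurable lesions: "The most reproducible measurable lesions, up to a maximum of 2 lesions per organ and 5 lesions in total". PR is "At least a 30% decrease in the sum of diameters of target lesions, taking as reference the baseline sum diameters". For non-target disease, the category between CR and progression is Non-CR/Non-PD: "Persistence of one or more non-target lesions and/or persistence of tumor marker level above the normal limits".

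**Endpoint rules.** In Section 9.5.3, ORR counts CR or PR, and DCR counts CR, PR or SD. Patients with no adequate post-baseline assessment are NE and count as non-responders. The only definition of an adequate assessment, given under DOR, is one read as CR, PR or SD.

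**The concern.** A patient without a measurable lesion has no target lesion and no baseline sum of diameters, so PR is not available. Unless all disease disappears, the best result is Non-CR/Non-PD. The patient stays in the ORR denominator with almost no way into the numerator. The effect runs in one direction only: the ORR falls relative to that in patients whose response can be measured.

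The same gap touches DCR. Non-CR/Non-PD is not in the DCR definition and, read literally, is not an adequate assessment either. A patient whose non-target disease is simply holding would then be NE.

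Part A objective response is a stated secondary endpoint (Table 4), and Section 4.1 names preliminary antitumor activity among the inputs to the RP2D. A reader of the Part A report would need to know which denominator lies behind the figure.

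**Working it through.** **Inputs**
- Dose escalation: about 60 DLT-evaluable patients, accelerated titration excluded (synopsis, Section 9.3.1).
- Accelerated titration: 4 single-patient cohorts (synopsis, Section 4.1).
- Food-Effect: about 16 PK-evaluable patients.
- Safety Expansion: up to about 48 patients.
- Stated Part A total: about 128.

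**The plan's own figure.** 60 + 48 + 16 = 124, which falls short of 128. Adding the 4 titration patients gives 128. No sample size, power or target ORR is stated for Part A efficacy, so this denominator is the only planned figure to reproduce.

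**Patients with no measurable-disease requirement.** 60 + 4 + 16 = 80, and 80/128 = 62.5%. The number dosed could be higher. The 60 and 16 are evaluable patients, and a dosed patient who is replaced remains in the FA population.

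**Dilution.** Let p be the ORR in patients with measurable disease and f the share of the 80 without it. CR in non-target-only disease is taken as about 0.
- Affected cohorts: p × (1 − f)
- Combined Part A: p × (128 − 80f)/128 = p × (1 − 0.625f)

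The documents do not give f, so 10, 20 and 30% are assumptions.

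| f | Patients without measurable disease | p = 20%: affected cohorts | p = 20%: combined | p = 30%: affected cohorts | p = 30%: combined |
|---|---|---|---|---|---|
| 10% | 8 | 18% | 18.8% | 27% | 28.1% |
| 20% | 16 | 16% | 17.5% | 24% | 26.3% |
| 30% | 24 | 14% | 16.3% | 21% | 24.4% |

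Example, p = 20% and f = 20%, combined: 0.20 × (128 − 16)/128 = 0.175. If 2% of the non-measurable patients reached CR, this would be (0.20 × 112 + 0.02 × 16)/128 = 17.75%, so allowing for a few CRs changes little.

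**Against sampling error.** With 22 responders, 22/128 is 17.2% (exact 95% CI 11.1 to 24.9%) and 22/112 is 19.6% (12.7 to 28.2%). The shift is smaller than the interval, but unlike sampling error it always goes the same way.

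**Does another set repair it?** The PPE population asks for eligibility and for baseline and post-baseline response assessments, not for measurable disease. It is also reserved for exploratory sensitivity analyses. Section 9.4 defines no response-evaluable set.

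**The case against.** The strongest reply is that this is a descriptive secondary endpoint with no hypothesis test, and that an all-treated response proportion is a legitimate, conservative summary. Not being required to have measurable disease is also not the same as lacking it, and nothing in the documents shows that any such patient was dosed. Cohorts are small. Results are given by cohort as well as combined, so the Safety Expansion figure can be read alone. The combined figure already pools many doses and two schedules. All of this stands: it limits the size and urgency of the point, and it makes the dilution conditional.

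Section 9.1 also leaves detail on endpoints to the SAP. If that text defines a response-evaluable set, Sections 9.4 and 9.5.3 need only refer to it. The document supplied contains no such definition.

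Three stronger readings are tempting and are not supported:
- **That cohorts differ in their share of non-measurable disease, so cohort comparisons are confounded.** No section reports this share for any cohort, and no between-cohort efficacy test is planned.
- **That this ORR decides whether central reading takes place.** Section 5.3.3 does ask that scans be available "for a future central reading by a BICR committee depending on preliminary efficacy results from Part A". It does not name the combined FA ORR, however, and BICR is committed without that condition in Sections 9.2, 9.5.3 and 10.3.3.
- **That DOR needs the same restriction.** DOR is already limited to responders, so restricting it would change nothing or would remove a genuine CR.

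**Conclusion.** The point holds in conditional form. Part A ORR uses all dosed patients, about 80 of 128 have no measurable-disease requirement, and PR is defined only on measurable target lesions. If patients without target lesions were dosed, the ORR in the dose-escalation, titration and Food-Effect cohorts falls by a factor of about 1 − f, and the combined ORR by about 1 − 0.625f. At f = 30% the relative loss is 30% and about 19%; at f = 10% it is 10% and about 6%.

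These sizes rest on an assumed f and on CR being rare in non-target-only disease. The direction rests on the text alone. The Safety Expansion's own ORR is untouched, and so is the Part B primary analysis, because criterion 17 requires measurable disease there. This is a cheap improvement to a secondary endpoint, not a threat to the trial's main conclusion.

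**What to change.** Change the Part A sentence in Section 9.5.3, and add the matching set to Section 9.4, as follows:
- Report Part A ORR, by cohort and combined, in FA patients with at least one measurable lesion at baseline.
- Show the all-FA ORR alongside, with the number of patients without measurable disease in each cohort.
- List any CR in non-target-only disease.
- State whether Non-CR/Non-PD counts towards DCR and whether it is an adequate tumor assessment. The second answer also settles PFS censoring dates for these patients.
- Leave the DOR, PFS and OS analysis sets as they are.

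Section 1.1.7 reports 65 Part A patients already dosed by 02 April 2021, so the remedy belongs in the analysis rather than in eligibility. It takes a few sentences and one flag derived from baseline lesion data that Appendix B already has recorded. The cost is a slightly smaller denominator, and any CR in non-target-only disease drops out of the restricted ORR, which is why the all-FA figure and the list should stay. Settling this before the analysis avoids a post hoc choice of denominator.

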9.5.4. Sub-group Analyses

Subgroups will be explored for the primary efficacy endpoint based on:

- Mutation clusters within a cohort.
- Tumor types across cohorts, such as NSCLC, breast cancer, colorectal cancer, and other cancer types regardless of mutation variant.
- Mutation variants across cohorts such as [REDACTED], [REDACTED] separate, as data permit), other [REDACTED] mutations, and [REDACTED] mutations regardless of tumor type.

Other subgroups may be explored for the primary and secondary efficacy endpoint as described in the SAP.

9.5.5. Safety Analysis

Safety will be assessed through the analysis of the reported incidence of TEAEs. Treatment emergent AEs are those with an onset on or after the initiation of therapy (on or after C1D1, first dose of study drug) and will be graded according to NCI [CTCAE Version 5.0](#).

The TEAEs will be coded using the current version of Medical Dictionary for Regulatory Activities (MedDRA; <https://www.meddra.org/about-meddra/>) and summarized using system organ class and preferred term for all patients in the FA population. In addition, summaries of SAEs, TEAEs leading to treatment discontinuation, TEAEs by maximum NCI CTCAE grade, and TEAEs related to study treatment will also be presented. TEAEs will be summarized separately for Part A and Part B. In Part A, the TEAE summary will be provided by dose level, cohort, and overall, whereas in Part B, the TEAE summary will be provided by cohort, subgroups within a cohort (as appropriate), and overall. Additional TEAE analysis (such as subset or pooled analysis) could be performed if data warrants.

Other safety endpoints including laboratory results, vital signs, physical examinations, ECG findings, and cardiac function will be summarized for all patients in the FA population and presented separately for Parts A and B, respectively. Descriptive summary statistics of observed values, as well as changes from baseline, will be presented. In addition, laboratory parameters will also be summarized by shift from baseline CTCAE grade to maximum post-baseline CTCAE grade ([NCI CTCAE Version 5.0](#)).

Concomitant medications will be coded using the World Health Organization Drug Dictionary (WHO DD; <https://www.who-umc.org/>) and they will be listed and summarized for Part A and Part B separately.

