5.3.1. Food-effect Assessment (Dose Escalation Part A)

The effect of food on the PK of BDTX-189 will be assessed in a single dose, fed/fasted randomized crossover design. Based on the projected exposures at the various dose levels, Food Effect evaluation is planned at dose level 5 (400 mg QD). Randomization will be performed by Development Innovations at the time of patient registration. The Food Effect evaluation will be executed without disruption of the Dose Escalation and DLT evaluation to the extent feasible. Dose level 5 (400 mg QD) will therefore proceed as described in Section 4.3.1 in patients not having Food Effect assessed. Assignment of 3 or more patients to dose level 5 (400 mg QD) for DLT assessment will take place according to Section 4.3.2.

Patients (n = up to 8 per meal type) will be assigned to the Food Effect evaluation as described below. Depending on emerging data, additional patients may be enrolled to meet the requirements of a pivotal Food Effect study. The SRC will decide how to allocate patients but should prioritize assignment of patients for DLT evaluation. Patients evaluated for Food Effect will not be counted in the Boin decision rule. Should any DLT occur in the Food-effect Cohort, this will not be included in the dose escalation/de-escalation rules in Table 6, but the SRC will take the information into account for the dose increment/decrement decisions. Once the Day -1 assessments are complete, the patients may continue study drug administration on C1D1. The dose will be 400 mg QD unless that dose level has been declared tolerated, and a decision made to escalate to dose level 6 (800 mg QD), in which case patients will be assigned to that dose level. Patients included in the Food Effect evaluation will not have additional PK samples collected on C1D1.

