Patients will receive BDTX-189 as a single oral dose on Day -4 after fasting for at least 10 hours before dosing or immediately after consuming a high-fat breakfast. Patients will receive BDTX-189 in the opposite prandial state on Day -1. BDTX-189 will be administered QD in 21-day cycles starting on C1D1. On the assigned day of PK assessment in the fed state, 30 minutes prior to the planned BDTX-189 administration time, patients will be instructed to consume a high-fat meal (see below for an example breakfast) and must finish the meal within 30 minutes. Patients will be instructed to take their dose of BDTX-189 with approximately 240 mL water within 30 minutes after starting the high-fat meal. On the assigned day of PK assessment in the fasted state, BDTX-189 will be administered together with approximately 240 mL water, following an overnight fast of at least 10 hours. Patients should not consume any food for at least 4 hours after the dose. The use of agents that suppress gastric acidity (H2 receptor antagonists, proton pump inhibitors, and intraluminal antacids) and agents that delay gastric emptying are prohibited from 1 week prior to the Day -4 dose until C1D1, when only proton pump inhibitors will be prohibited, as described in Section 4.5.2. Please see Table 11 (PK Sample Collection Food Effect Part A) for specific time points.

Patients will be given a high-fat breakfast in order to assess food effects on the PK of BDTX-189. An example high-fat breakfast that will be provided is a standard McDonald's

breakfast, which might include an Egg McMuffin, bacon, hash browns, and milk. Note: Alternative food components/quantity and/or time (i.e., lunch) may be allowed as per timing of dose administration and as approved by the Investigator/Sponsor. In addition, a low-fat breakfast may also be assessed as emerging data dictate. An example low-fat breakfast may include 8 ounces of milk (1% fat), one boiled egg, and one packet flavored instant oatmeal with water (approximately 400-500 calories).

5.3.2. *Electrocardiogram Measurements*

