8.1.5. Recording and Reporting of Adverse Events

Recording of Adverse Events

All AEs of any patient during the course of the research study will be recorded in the eCRF, and the Investigator will give his or her opinion as to the relationship of the AE to the study drug treatment (i.e., whether the event is related or unrelated to study drug administration).

All AEs should be documented in the eCRF. A description of the event, including its date of onset and resolution, whether it constitutes an SAE or not, any action taken (e.g., changes to study treatment), and its outcome should be provided, along with the Investigator’s assessment of causality (i.e., the relationship to the study treatment). For an AE to be a suspected treatment-related event, there should be at least a reasonable possibility of a causal relationship between the protocol treatment and the AE. Adverse events will be graded according to the NCI [CTCAE Version 5.0](#), and changes in severity will be documented by recording the AE as separate entries.

If the AE is serious, it should be reported within 24 hours of the Investigator site awareness or receipt of the initial SAE or any follow-up information to Development Innovations Safety Department. Other untoward events occurring in the framework of a clinical study are to be recorded as AEs (i.e., AEs that occur prior to assignment of study treatment that are related to a protocol-mandated intervention, including invasive procedures such as biopsies, medication washout, or no treatment run-in).

Test findings will be reported as an AE if the test result requires an adjustment in the study drug or discontinuation of treatment and/or test findings require additional testing or surgical intervention, a test result, or finding is associated with accompanying symptoms, or a test result is considered to be an AE by the Investigator.

Reporting Period for Adverse Events

All AEs, regardless of seriousness or relationship to study treatment, spanning from the signing of the ICF until 30 calendar days after discontinuation or completion of study treatment as defined by the study for that patient after his/her last dose of BDTX-189, are to be recorded on the AE page in the eCRF. The AEs occurring from the signing of the ICF until the first dosing with BDTX-189 will be the pre-treatment AEs. The AEs occurring at or after the first dosing will be the TEAEs.

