9.3. Sample Size Considerations

9.3.1. Phase 1 (Part A)

The Phase 1 dose-escalation portion of the study will utilize a BOIN design as described in Section 4.3.1 and [Appendix G](#). Part A will enroll approximately 36 DLT-evaluable patients to the QD schedule, and approximately 24 additional DLT-evaluable patients may be treated in the dose-escalation portion to assess the BID schedule. The number of DLT-evaluable patients in Part A will not exceed 60, excluding patients in the accelerated titration step. Because both a QD and BID schedule are being evaluated and one RP2D and schedule will be selected, the Safety Expansion cohort(s) will include up to 48 patients, including a minimum of 12 patients for PK evaluation of a smaller and reformulated 200 mg tablet. In addition, up to 16 PK-evaluable patients will be enrolled to evaluate food-effect for a total of up to approximately 128 evaluable patients in Part A. The final sample size will depend on the dosing schedule, the number of DLTs, and the total number of cohorts treated before a DLT is observed and the MTD is determined.

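### Section 9.5.5 starts TEAEs at C1D1, but Food-Effect patients take their first BDTX-189 dose on Day -4, in conflict with Section 8.1.5

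*Combined protocol and SAP*

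**What the plan says.** Section 9.5.5 (Safety Analysis) sets the rule for the safety tables: "Treatment emergent AEs are those with an onset on or after the initiation of therapy (on or after C1D1, first dose of study drug". It summarizes TEAEs in the Full Analysis (FA) population, in Part A by dose level, cohort and overall.

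Section 8.1.5 (Recording and Reporting of Adverse Events) makes the same split with no reference to C1D1: "The AEs occurring from the signing of the ICF until the first dosing with BDTX-189 will be the pre-treatment AEs", and "The AEs occurring at or after the first dosing will be the TEAEs".

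Section 5.3.1 describes the Food-Effect lead-in: "Patients will receive BDTX-189 as a single oral dose on Day -4". The second dose follows "in the opposite prandial state on Day -1. BDTX-189 will be administered QD in 21-day cycles starting on C1D1". For these patients C1D1 is a continuation: "Once the Day -1 assessments are complete, the patients may continue study drug administration on C1D1".

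Section 9.3.1 gives the size of the cohort: "up to 16 PK-evaluable patients will be enrolled to evaluate food-effect for a total of up to approximately 128 evaluable patients in Part A".

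Section 9.4 places anyone with at least one dose in the FA population. Table 4 lists TEAE incidence and severity, including DLTs, as the Part A primary endpoint, and TEAE incidence as a secondary safety endpoint for both parts.

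**The concern.** The parenthesis in Section 9.5.5 treats C1D1 and the first dose as the same day. That is true for every patient except those in the Food-Effect cohort, who have already had two single doses by C1D1. Sections 9.5.5 and 8.1.5 therefore give different start dates for that cohort, and 9.5.5 is the section a programmer will work from.

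A literal C1D1 cut-off is a realistic risk. It is the only visit named in the definition, and Table 1 also makes C1D1 the anchor of the visit calendar. Under that cut-off, an AE that follows drug exposure on Day -4 to Day -1 is not a TEAE, while the patient still counts in the denominator. A patient who stopped after a lead-in dose would be in the FA population with no possibility of a TEAE.

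Baseline has the same weakness. Section 9.5.5 calls for change from baseline and CTCAE shift summaries but does not define baseline. Table 1 schedules no laboratory tests or ECG on Day -4 or Day -1. If a C1D1 pre-dose value served as baseline for these patients, it would follow two doses of drug.

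**Working it through.** The plan states no figure on this point, so the check is a comparison of dates followed by simple arithmetic.

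**1. How an AE with onset in the lead-in is classed (Food-Effect patient, after the Day -4 dose and before C1D1)**

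| Text | Anchor | Classification |
|---|---|---|
| Section 8.1.5 | first dosing with BDTX-189 = Day -4 | TEAE |
| Section 9.5.5, the first-dose words | first dose = Day -4 | TEAE |
| Section 9.5.5, the named visit | C1D1 | not a TEAE |

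For all other patients the first dose is on C1D1 and the three readings agree.

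**2. Length of the disputed window.** Day -4 to Day -1 is 4 calendar days if there is no Day 0, and 5 if there is one. The documents do not say. The window holds 2 single doses per patient.

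**3. Patients affected** (Section 9.3.1). At most 16 / 128 = 0.125, or 12.5% of Part A.

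**4. Effect on incidence.** Let q be the share of the 16 patients who have a given event with onset only in the lead-in. The documents give no such rate, so q is an assumption.

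- Patients lost = 16 × q
- Fall in overall Part A incidence = 16 × q / 128
- Fall in the Food-Effect cohort's own row = 16 × q / 16 = q

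| q (assumed) | Patients lost | Fall, Part A overall | Fall, Food-Effect row |
|---|---|---|---|
| 0.10 | 1.6 | 1.6 / 128 = 1.25 points | 10 points |
| 0.25 | 4 | 4 / 128 = 3.1 points | 25 points |
| 1.00 (upper limit) | 16 | 16 / 128 = 12.5 points | 100 points |

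**5. Are the data there?** Yes. Table 1 and Section 8.1.5 collect AEs from signature of the consent form, so lead-in events are recorded. Only their classification is at stake.

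**6. Effect on dose finding.** None on the estimate. Sections 4.3.2.1 and 9.4 keep Food-Effect patients out of the DLT-evaluable population, and Section 5.3.1 keeps them out of the BOIN decision rule.

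**The case against.** The strongest reply is that this is one misplaced visit label. The leading words of the 9.5.5 sentence refer to the start of therapy, and the parenthesis also says first dose. Both mean Day -4 for this cohort. Section 8.1.5 is unambiguous, and Section 9.1 leaves further detail to the SAP. Misclassification needs a programmer to follow the label over everything else. That is fair, and it is why the loss of events is conditional. It does not make the label right: the date is wrong for a whole cohort, and nothing in the text available settles which anchor governs.

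Several stronger readings are tempting, and the documents do not support them:

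- **That lead-in events would be classed as pre-treatment.** Section 8.1.5 holds the only definition of pre-treatment AEs and ends that period at first dosing.
- **That ongoing lead-in events would become baseline conditions.** All AEs from consent onward go on the AE page (Section 8.1.5). Under Section 8.2.2 a recurrence or a change in severity is a separate entry, so such an event could still count after C1D1.
- **That many gastrointestinal events would be lost, given 58.5% diarrhea and 47.7% nausea in Section 1.1.7.** Those are whole-treatment incidences across regimens up to 1200 mg QD and 800 mg BID. The lead-in is two single 400 mg doses over about four days.
- **That 12 of the 65 patients treated at the data cut were affected.** Section 1.1.7 gives 6 evaluable patients in each of two food-effect cohorts, but does not say how many of the 65 were Food-Effect patients.
- **That the MTD is biased.** The Part A primary estimand in Section 9.2 is the DLT rate, and these patients do not enter it.

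**Conclusion.** The point holds as an inconsistency with a conditional consequence. The C1D1 anchor in Section 9.5.5 is wrong for up to 16 of about 128 Part A patients and disagrees with Section 8.1.5. If it is programmed literally, events with onset only in the lead-in leave the TEAE tables. At an assumed 10% or 25% of the cohort, that is 1.6 or 4 patients per event term, or 1.25 or 3.1 percentage points overall, with 12.5 points as the upper limit. The size rests on full enrollment of 16, a denominator of 128, and an assumed q that the documents cannot supply.

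What is exposed is the descriptive TEAE reporting for Part A. The DLT rate, the BOIN decisions and the MTD estimate do not change. The tables still matter: TEAE incidence and severity are named in the Part A primary endpoint, and Section 4.3.2.1 has safety information from these patients considered in escalation and RP2D decisions. The inconsistency is certain from the text. An actual undercount is not.

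**What to change.** In Section 9.5.5, remove C1D1 from the definition. Define TEAEs as AEs with onset on or after the first dose of BDTX-189, including Food-Effect lead-in doses. This matches Section 8.1.5.

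Add one sentence on baseline: for the Food-Effect cohort, baseline for laboratory, ECG and shift summaries is the last value before that first dose. Since Table 1 has no laboratory tests or ECG on Day -4 or Day -1, this will normally be the screening value.

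Because Part A tables are split by dose level, it would also help to state the level under which lead-in events are shown. The lead-in dose is 400 mg (Section 4.1), while Section 5.3.1 allows these patients to start C1D1 at 800 mg.

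The cost is two or three sentences and the matching programming specification. No new data are needed, and nothing changes for patients whose first dose is on C1D1.
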